7.1.1 Analysis of AE data

Analysis of AE data will primarily be descriptive based on MedDRA coding of events. The proportion of subjects experiencing an SAE and the proportion experiencing a Grade 3 or higher AE will be compared between randomized arms using Fisher's Exact Test.

7.1.2 Analysis of anti-SARS-CoV-2 titers

Analysis of titers will also primarily be descriptive, comparing the geometric mean titers at days 0, 1, 3, 7 and 14 between the randomized arms.

8. Endpoints

Primary Endpoint: Avoidance of new or ongoing ICU admission.

Secondary endpoints:

1. Cardio-circulatory arrest (at any time)
2. Transfer to ICU
3. Type and duration of respiratory support (and other ICU support) in ICU
4. ICU mortality and LOS
5. Hospital mortality and LOS
6. Ventilator-free days
7. 60 day mortality

Primary Safety Endpoints:

- Rapid deterioration of respiratory or clinical status on transfusion of SARS-CoV-2 convalescent plasma
- Cumulative incidence of serious adverse events during the study period: transfusion reaction (fever, rash), transfusion related acute lung injury (TRALI), transfusion associated circulatory overload (TACO), transfusion related infection

Secondary Endpoints

1. Anti-SARS-CoV-2 titers at days 0, 1, 3, 7 and 14.
2. Rates and duration of SARS-CoV-2 PCR positivity (RT-PCR) at days 0, 3, 7, and 14.

9. Study procedures

Day -1 to 0:

- A. Screening (must be completed before randomization)
- B. Subject informed consent (obtained before performing study related activities)
- C. Baseline Evaluation (at screening) (much of the information will be obtained from the medical record)
 1. Demographics (Age, sex ethnicity, race)
 2. Medical history (timing of exposure to COVID-19 source patient, acute and chronic medical condition, medications, allergies. Any medical condition arising after consent should be recorded as AE)
 3. COVID-19 symptom screen (fevers, cough, shortness of breath), onset of symptoms, source of contagion
 4. Vital signs
 5. COVID-19 testing (RT-PCR) from nasopharyngeal, throat, tracheal aspirate or broncho alveolar lavage and stool (optional) samples
 6. Blood typing, CBC, comprehensive metabolic panel
 7. Serological testing: anti-SARS CoV-2 titers
 8. Stored samples for future studies
 9. Urine or serum pregnancy test for females of childbearing potential. Results from laboratory tests obtained up to 7 days before enrollment may be used for the pregnancy test.
 10. Determination of eligibility as per inclusion/exclusion criteria age, consent, positive for COVID-19, respiratory symptoms, not already an ICU patient,, between day 3 and 7 of first sign of illness (or within 72 hours of admission)

DAY 0:

1. Randomization of eligible subjects
2. Study Plasma Administration: 1-2 units of plasma will be transfused. Time at start and end of infusion will be recorded and Vital signs will be measured immediately prior to infusion, 10-20 minutes after start of infusion, at completion of infusion and 30-60 minutes after the end of the infusion
3. COVID-19 symptom screen (fevers, cough, shortness of breath)
4. Assessment of clinical status (7-point ordinal scale)
5. New medical conditions, concomitant medication, AE evaluation
6. physical examination
7. COVID-19 testing (RT-PCR) from nasopharyngeal, throat and stool (optional) samples
8. Blood typing, CBC, comprehensive metabolic panel, C-reactive protein
9. Serological testing: anti-SARS CoV-2 titers
10. Stored samples for future studies (cytokines, CD4-CD8, HLA-DR)

Day 1-7 (or for duration of hospitalization)

1. Vital signs daily
2. COVID-19 symptom screen (fevers, cough, shortness of breath)
3. Assessment of clinical status (7-point ordinal scale)
4. New medical conditions, AE evaluation
5. physical examination
6. CBC, comprehensive metabolic panel, CRP daily
7. Serological testing: anti-SARS CoV-2 titers
8. Stored samples for future studies

Day 28:

Key issues to consider f/u by phone, alive, at home, in hospital (ICU or not), on supplemental O2 or not, back to work, fully, partially, SNF, nursing home, LTAC0

1. COVID-19 symptom screen (fevers, cough, shortness of breath)
2. Assessment of clinical status (7-point ordinal scale)
3. New medical conditions, AE evaluation

Day 60 and 90:

1. COVID-19 symptom screen (fevers, cough, shortness of breath)
2. Assessment of clinical status (7-point ordinal scale)
3. New medical conditions, AE evaluation

10. Efficacy, virology and PK measures

Clinical Efficacy (ordinal scale)

1. Death/Cardio-circulatory arrest at anytime
2. Transfer to ICU
3. Type and duration of respiratory support (and other ICU support)in ICU
4. ICU mortality and LOS
5. Hospital mortality and LOS
6. Ventilator-free days
7. 28 day mortality

Virologic measures

1. Rates, levels and duration of SARS-CoV-2 RNA in NP swabs by RT-PCR at days 0, 3, 7 and 14. Other specimen types may be tested as available (eg., BAL fluid, tracheal secretions, sputum, etc.) or when RT-PCR assays are validated for additional sources (i.e., stool, blood).

2. Serologic positivity and neutralization antibody titers for anti-SARS-CoV-2 at days 0, 1, 3, 7 and 14 (additional days 21 and 28 may be included, as available).

11. Risks and benefits

Potential Benefits of treatment:

The potential benefits of antiviral treatment with anti-SARS CoV-2 plasma in patients with respiratory symptoms consistent with interstitial pneumonia at high risk for requiring ICU admission are not known. However, it is anticipated that treatment will decrease the risk of disease progression requiring ICU admission and aggressive respiratory support including possible mechanical ventilation (and other ICU support).

Potential benefits of clinical monitoring and virologic testing:

Subjects enrolled in the study may reduce their chances of disease progression.

Potential risks:

1. Risks of plasma: Fever, chills, rash, headache, serious allergic reactions, TRALI, TACO, transmission of infectious agents
2. Risks of phlebotomy: local discomfort, bruising, hematoma, bleeding, fainting,
3. Total blood draws will not exceed 500 mL
4. Risks of oropharyngeal and throat swab: local discomfort, vomiting

Alternatives:

The alternative to participation in this study is routine care.

12. Safety measures

1. Safety Evaluations will assess for the safety of high titer anti-SARS-CoV-2 plasma and determine if it is higher, lower or the same as standard plasma
2. Clinical evaluations: Vital signs and symptom screen on days 0-7, 14 and symptom screens on days 28, 60, and 90.
3. Laboratory evaluations consistent with ongoing medical care may include radiographic imaging modalities such as chest x-rays and chest CT.
4. Safety laboratory tests (ABO typing, pregnancy testing, CBC, CRP, and comprehensive metabolic panel) will be performed at the local CLIA-certified clinical laboratory on days 0-7 and 14.

Event (AE)

Any untoward medical occurrence in a clinical investigation subject who has received a study intervention and that does not necessarily have to have a causal relationship with the study product. An AE can, therefore, be any unfavorable and unintended sign (including an abnormal laboratory finding, for

example), symptom, or disease temporally associated with the use of the study product, whether or not considered related to the study product.

Serious Adverse Event (SAE)

An SAE is any adverse event that results in any of the following outcomes:

1. Death
2. Life-threatening (immediate risk of death)
3. Prolongation of existing hospitalization
4. Persistent or significant disability or incapacity
5. Important medical events that may not result in death, be life threatening, or require intervention or escalation of care may be considered a serious adverse event when, based upon appropriate medical judgment, they may jeopardize the subject and may require medical or surgical intervention to prevent one of the outcomes listed in this definition. Examples of such medical events include allergic bronchospasm requiring intensive treatment in an emergency room or at home, blood dyscrasias or convulsions that do not result in inpatient hospitalization.

Unexpected Adverse event: (UAE) An adverse reaction, the nature or severity of which is not consistent with the investigator's brochure.

Serious and Unexpected Suspected Adverse Reaction (SUSAR)

Unanticipated Problem (UP)

Unanticipated Problem that is not an Adverse Event (e.g. breaches of confidentiality, accidental destruction of study records, or unaccounted-for study drug.

Protocol Deviation: Deviation from the IRB-approved study procedures. Designated serious and non-serious

1. Serious Protocol Deviation: Protocol deviation that is also an SAE and/or compromises the safety, welfare or rights of subjects or others
2. Safety Reporting Requirements

Reporting Interval

All AEs and SAEs will be documented from the first administration of study product until completion or un-enrollment from the study. All AEs and SAEs will be followed until resolution even if this extends beyond the study-reporting period. Resolution of an adverse event is defined as the return to pre-treatment status or stabilization of the condition with the expectation that it will remain chronic.

At any time after completion of the study, if the investigator becomes aware of a SAE that is suspected to be related to study product

Investigator's Assessment of Adverse Events

The determination of seriousness, severity, and causality will be made by an on-site investigator who is qualified (licensed) to diagnose adverse event information, provide a medical evaluation of adverse events, and classify adverse events based upon medical judgment. This includes but is not limited to physicians, physician assistants, and nurse practitioners.

Laboratory abnormalities will be reported as AEs if there is a 2 s.d. increase above baseline.

Assessment of Seriousness

1. Event seriousness will be determined according to the protocol definition of an SAE
2. Assessment of Severity

Event severity will be assigned according to the scale below

- 1 = Mild: Transient or mild discomfort (<48 hours); no medical intervention/therapy required.)
- 2 = Moderate: Some worsening of symptoms but no or minimal medical intervention/therapy required)
- 3 = Severe: Escalation of medical intervention/therapy required
- 4 = Life-threatening: Marked escalation of medical intervention/therapy required.
- 5= Death

Assessment of Association

The association assessment categories that will be used for this study are:

- Associated – The event is temporally related to the administration of the study product and no other etiology explains the event.
- Not Associated – The event is temporally independent of the study product and/or the event appears to be explained by another etiology.

The investigator must provide an assessment of association or relationship of AEs to the study product based on:

- Temporal relationship of the event to the administration of study product;
- Whether an alternative etiology has been identified;
- Biological plausibility;
- Existing therapy and/or concomitant medications.

13. Safety Oversight

Monitoring Plan

1. All AE and SAW will be reviewed by protocol team in real time.
2. A medical monitor will be appointed by the sponsor for safety oversight of the clinical study.
3. A data safety monitoring board (DSMB), led by **[name]** composed of independent experts without conflict of interests will be established. The Board will review the study before initiation and at least yearly thereafter. The Board will review study data to evaluate the safety, efficacy, study progress, and conduct of the study
4. An Independent Safety Monitor (ISM) will be appointed. The ISM is a physician with expertise in infectious diseases and whose primary responsibility is to provide timely independent safety monitoring. An ISM is in close proximity to the study site and has the authority to readily access study participant records. The ISM reviews any SAE that occurs at the study site in real time and provides a written assessment.

Study monitoring

1. As per ICH-GCP 5.18 and FDA 21 CFR 312.50, clinical protocols are required to be adequately monitored by the study sponsor. Monitors will verify that
 - a. There is documentation of the informed consent process and signed informed consent documents for each subject
 - b. There is compliance with recording requirements for data points
 - c. All SAEs are reported as required
 - d. Individual subjects' study records and source documents align
 - e. Investigators are in compliance with the protocol.
 - f. Regulatory requirements as per Office for Human Research Protections-OHRP), FDA, and applicable guidelines (ICH-GCP) are being followed.

Halting Criteria for the Study

The study enrollment and dosing will be stopped and an ad hoc review will be performed if any of the specific following events occur or, if in the judgment of the study physician, subject safety is at risk of being compromised:

1. Death within one hour of plasma infusion
2. Occurrence of a life-threatening allergic/hypersensitivity reaction (anaphylaxis), manifested by bronchospasm with or without urticaria or angioedema requiring hemodynamic support with pressor medications or mechanical ventilation. , TRALI, TACO
3. One subject with an SAE associated with study product.
4. Two subjects with a Grade 3 or higher lab toxicity for the same parameter associated with study product.
5. An overall pattern of symptomatic, clinical, or laboratory events that the medical monitor, ISM, or SMC consider associated with study product and that may appear minor in terms of individual events but that collectively may represent a serious potential concern for safety.
6. Any other event(s) which is considered to be a serious adverse event in the good clinical judgment of the responsible physician. This will be appropriately documented.

Upon completion of this review and receipt of the advice of the ISM or SMC, DMID will determine if study entry or study dosing should be interrupted or if study entry and study dosing may continue according to the protocol.

Halting Criteria/Rules for Subject Infusion

Infusion of study drug will be halted if any of the following manifestations of anaphylaxis develop and will not be restarted:

- Skin or mucous membrane manifestations: hives, pruritus, flushing, swollen lips, tongue or uvula
- Respiratory compromise: dyspnea, wheezing, stridor, hypoxemia
- A decrease in systolic blood pressure to < 90 mmHg or >30% decrease from baseline or a diastolic drop of >30% from baseline.
- Tachycardia with an increase in resting heart rate to > 130bpm; or bradycardia <40 that is associated with dizziness, nausea or feeling faint.

- Any other symptom or sign which in the good clinical judgment of the study clinician or supervising physician warrants halting the infusion. For example, the rapid onset of gastrointestinal symptoms, such as nausea, vomiting, diarrhea, and cramps, for instance, may be manifestations of anaphylaxis and may warrant an immediate halt prior to meeting full SAE criteria

14. Ethics/Protection of human subjects

1. Ethical Standard

The Mayo Clinic is committed to the integrity and quality of the clinical studies it coordinates and implements. Mayo will ensure that the legal and ethical obligations associated with the conduct of clinical research involving human subjects are met. The information provided in this section relates to all Mayo sites participating in this research study

As the Department of Health and Human Services continues to strengthen procedures for human subjects' protections via new regulations, Mayo will review these evolving standards in relation to the proposed activities and will advise the investigators on those that may apply.

In addition, Mayo has a Federal wide Assurance (FWA) number on file with the Office for Human Research Protections (OHRP).

This assurance commits a research facility to conduct all human subjects' research in accordance with the ethical principles in The Belmont Report and any other ethical standards recognized by OHRP. Finally, per OHRP regulations, the research facility will ensure that the mandatory renewal of this assurance occurs at the times specified in the regulations.

2. Institutional Review Board

The Mayo IRB will review this protocol and all protocol-related documents and procedures as required by OHRP and local requirements before subject enrollment. The Mayo IRB currently holds and will maintain a US FWA issued by OHRP for the entirety of this study.

3. Informed Consent Process

The informed consent process will be initiated before a volunteer agrees to participate in the study and should continue throughout the individual's study participation. The subject will sign the informed consent document before any procedures are undertaken for the study. A copy of the signed informed consent document will be given to the subject for their records. The consent will explain that subjects may withdraw consent at any time throughout the course of the trial. Extensive explanation and discussion of

risks and possible benefits of this investigation will be provided to the subjects in understandable language. Adequate time will be provided to ensure that the subject has time to consider and discuss participation in the protocol.

The consent will describe in detail the study interventions/products/procedures and risks/benefits associated with participation in the study. The rights and welfare of the subjects will be protected by emphasizing that their access to and the quality of medical care will not be adversely affected if they decline to participate in this study.

4. Subject Confidentiality

Subject confidentiality is strictly held in trust by the participating investigators, their staff, and the sponsors and their agents. No information concerning the study or the data will be released to any unauthorized third party without prior written approval of the sponsor. The results of the research study may be published, but subjects' names or identifiers will not be revealed. Records will remain confidential. To maintain confidentiality, the PI will be responsible for keeping records in a locked area and results of tests coded to prevent association with subjects' names. Data entered into computerized files will be accessible only by authorized personnel directly involved with the study and will be coded. Subjects' records will be available to the FDA, the NIH, the manufacturer of the study product and their representatives, investigators at the site involved with the study, and the IRB.

15. Future Use of Stored Specimens

Subjects will be asked for consent to use their samples for future testing before the sample is obtained. The confidentiality of the subject will be maintained. They will be no plans to re-contact them for consent or to inform them of results. The risk of collection of the sample will be the small risk of bruising or fainting associated with phlebotomy however these samples will be taken at the same time as other protocol required samples.

No human genetic testing will be performed on the samples.

Five ml of blood samples will be collected at 5 time points (See Schedule of Events). Serum will be frozen in 1-ml aliquots. These samples will be used to answer questions that may arise while the study is underway or after it is completed. If for instance, there were unanticipated AEs, serum could be used to run tests that might help determine the reason for the AEs. Cytokines could be measured, for example.

Samples would not be shared with investigators other than investigators at Mayo unless outside investigators had relevant assays or expertise not available to the study investigators. The specimens would remain linked and at Mayo for 5 years. Any use of these specimens not specified in the current protocol will be reviewed by the Mayo IRB.

16. Data management and monitoring

a. Source Documents

The primary source documents for this study will be the subjects' medical records. If the investigators maintain separate research records, both the medical record and the research records will be considered the source documents for the purposes of auditing the study. The investigator will retain a copy of source documents. The investigator will permit monitoring and auditing of these data, and will allow the sponsor, IRB and regulatory authorities access to the original source documents. The investigator is responsible for ensuring that the data collected are complete, accurate, and recorded in a timely manner. Source documentation (the point of initial recording of information) should support the data collected and entered in to the study database and must be signed and dated by the person recording and/or reviewing the data. All data submitted should be reviewed by the site investigator and signed as required with written or electronic signature, as appropriate. Data entered into the study database will be collected directly from subjects during study visits or will be abstracted from subjects' medical records. The subjects' medical records must record their participation in the clinical trial and what medications (with doses and frequency) or other medical interventions or treatments were administered, as well as any AEs experienced during the trial.

Data Management Plan

Study data will be collected at the study site(s) and entered into the study database. Data entry is to be completed on an ongoing basis during the study.

b. Data Capture Methods

Clinical data will be entered into a database which includes password protection and internal quality checks to identify data that appear inconsistent, incomplete, or inaccurate.

c. Study Record Retention

The PI is responsible for retaining all essential documents listed in the ICH GCP Guidelines. The FDA requires study records to be retained for up to 2 years after marketing approval or disapproval (21 CFR 312.62), or until at least 2 years have elapsed since the formal discontinuation of clinical development of the investigational agent for a specific indication. These records are also to be maintained in compliance with IRB/IEC, state, and federal medical records retention requirements, whichever is longest. All stored records are to be kept confidential to the extent provided by federal, state, and local law. It is the site investigator's responsibility to retain copies of source documents until receipt of written notification to the sponsor.

No study document should be destroyed without prior written agreement between the sponsor and the Principal Investigator. Should the investigator wish to assign the study records to another party and/or move them to another location, the site investigator must provide written notification of such intent to sponsor with the name of the person who will accept responsibility for the transferred records and/or their new location. The

sponsor must be notified in writing and written permission must be received by the site prior to destruction or relocation of research records.

References

3. Zhang J-S, Chen J-T, Liu Y-X, Zhang Z-S, Gao H, Liu Y, et al. A serological survey on neutralizing antibody titer of SARS convalescent sera. *Journal of medical virology*. 2005;77(2):147–150.

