PROTOCOL SUMMARY:

Long title: Convalescent Plasma to Limit Coronavirus Associated Complications: A Randomized Open label, Phase 1 Study Comparing the Efficacy and Safety of High-Titer Anti-SARS-CoV-2 plasma vs. placebo in hospitalized patients with interstitial pneumonia due to COVID-19

Short title: CSSC-002

Clinical Phase: 1

IND Sponsor: Johns Hopkins via a national IND

Conducted by: Mayo Clinic in collaboration with Johns Hopkins University, Washington University in St. Louis and other interested parties.

Sample Size: 20

Study Population: Hospitalized COVID-19 patients aged 18 years of age with respiratory symptoms within 3 to 7 days from the beginning of illness.

Study Duration: April 1, 2020 to December 31, 2022

Study Design: This randomized placebo-controlled open label phase 1 trial will assess the efficacy and safety of anti-SARS-CoV-2 convalescent plasma in hospitalized patients with acute respiratory symptoms between 3 and 7 days after the onset of symptoms with or without confirmed interstitial COVID-19 pneumonia by chest CT. A total of 20 eligible subjects will be randomized in a 1:1 ratio to receive either high titer anti-SARS-CoV-2 plasma or control (standard thawed plasma)

The following will be assessed in all subjects:

- Age, sex, comorbidities, date of symptoms, source of infection, type of admission, APACHE score, SOFA score, Clinical status, vital signs including temperature, respiratory rate, oxygen saturation, oxygen requirement, CBC with neutrophil counts, lymphocytes count, CRP, chest x-ray, chest CT, location in hospital,
- Safety and efficacy: Day 0 (baseline), 1, 2, 3, 7, 14, and 28 and once monthly at 2-3 months.
- Serum or plasma antibody titer₁ to SARS-CoV-2: Day 0, 1, 3, 7, 14 (additional days 21 and 28 may be included, as available)

¹ Measured via initial anti-SARS-CoV-2 ELISA and serum neutralizing antibody titer to SARS-CoV-2.

- SARS-CoV-2 PCR from nasopharyngeal swabs: Day 0, 3, 7, 14 and at any time when there is clinical suspicion for COVID-19
- Outcome measures: increased O2 requirement (PaO2/FiO2 ratio or SpO2/Flo2), supplemental oxygen strategy (nasal cannula, , high flow nasal cannula, noninvasive ventilation, intubation and invasive mechanical ventilation, rescue ventilation i.e. neuromuscular blocking agents, prone positioning, corticosteroids, ECMO), vasopressors, renal support, ICU LOS, ICU mortality, Hospital LOS, Hospital mortality, 28 day mortality

Study Agent:

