- Pathogen reduced SARS-CoV-2 convalescent plasma (1-2 units; ~300-600 mL at neutralization antibody titer >1:64 *if possible* >1:160 *this is a moving target as assays develop*)
- Standard plasma²

Primary Efficacy Objective: Reduction in progression of oxygenation and ventilation support

Primary Endpoint: Avoidance of ICU admission.

Secondary endpoints:

1. Cardio-circulatory arrest (at any time)
2. Transfer to ICU
3. Type and duration of respiratory support (and other ICU support)in ICU
4. ICU mortality and LOS
5. Hospital mortality and LOS
6. Ventilator-free days
7. 28 day mortality

Primary Safety Objective: Evaluate the safety of treatment with high-titer anti-SARS-CoV-2 plasma versus control (standard plasma) in hospitalized patients with COVID-19 respiratory symptoms.

Primary Safety Endpoints:

1. Rapid deterioration of respiratory or clinical status on transfusion of SARS-CoV-2 convalescent plasma
2. Cumulative incidence of serious adverse events during the study period: transfusion reaction (fever, rash), transfusion related acute lung injury (TRALI), transfusion associated circulatory overload (TACO), transfusion related infection

² Solvent detergent treated pooled plasma

Secondary Objectives:

1. Compare the anti-SARS-CoV-2 convalescent plasma and control (standard plasma) groups anti-SARS-CoV-2 titers at days 0, 1, 3, 7 and 14 (additional days 21 and 28 may be included, as available).
2. Compare the rates, levels and duration of SARS-CoV-2 RNA in NP swabs using RT-PCR amongst the anti-SARS-CoV-2 convalescent plasma and control (standard plasma) groups at days 0, 3, 7 and 14. Other specimen types may be tested as available (eg., BAL fluid, tracheal secretions, sputum, etc.) or when RT-PCR assays are validated for additional sources (*i.e.*, stool, blood).

Study population:

Inclusion Criteria for Enrollment

1. Patients must be 18 years of age or older
2. Hospitalized with COVID-19 respiratory symptoms and confirmation via COVID-19 SARS-CoV-2 RT-PCR testing. Patient is willing and able to provide written informed consent and comply with all protocol requirements.
3. Patient agrees to storage of specimens for future testing.
4. If female must not be pregnant and/or breastfeeding.

Exclusion Criteria

1. Female subjects with positive pregnancy test, breastfeeding, or planning to become pregnant/breastfeed during the study period
2. Receipt of pooled immunoglobulin in past 30 days

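### The primary endpoint has no survival condition and no end day, so a ward death without ICU transfer reads as success; the mortality endpoint is 28-day in three places and 60-day in Section 8

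*Protocol*

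**What the plan says.** **Primary endpoint.** The Protocol Summary has "Primary Endpoint: Avoidance of ICU admission". Section 8 has "Primary Endpoint: Avoidance of new or ongoing ICU admission". The two differ in the words on new or ongoing admission, but neither mentions survival or gives an end day.

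**Starting point.** The eligibility step in Section 9 screens out patients who are already in the ICU.

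**Where death appears.** Death enters the efficacy measures only as separate items: ICU mortality, hospital mortality, fixed-day mortality, and the first item of the Section 10 list, which joins death with cardio-circulatory arrest. The corresponding first item in the Summary and in Section 8 names arrest only.

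**Mortality horizon.** The Summary's outcome measures end with "Hospital mortality, 28 day mortality". The Summary's secondary endpoints and the Section 10 list both have "7. 28 day mortality". The Section 8 list, with the same seven items in the same order, has "7. 60 day mortality".

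**Denominator.** Section 7.1 sets 20 patients in total and 10 per group as the default for percentages.

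**The concern.** The aim is to keep ward patients from getting worse, and Section 4 (potential benefits) names lower mortality as part of that aim. An endpoint that asks only whether the patient entered the ICU treats two very different patients alike: one who recovers on the ward and one who dies there. If a ward death takes the place of an ICU transfer, the arm's result improves. If it does not, the endpoint simply fails to register the death. In neither case does the headline proportion show what happened.

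The missing end day is a second gap in the same definition. Follow-up contacts fall at days 28, 60 and 90, and the result could depend on which of them closes the observation period.

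The mortality conflict matters for a similar reason. With two horizons for one listed endpoint, the choice between them could be made after the data are seen.

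**Working it through.** The protocol gives no event rate, effect size or power for the primary endpoint, so there is no design figure to reproduce. The check is textual, followed by an illustration.

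**Step 1: can a ward death occur under the definition?** Patients enter outside the ICU (Section 9). Success is the absence of ICU admission (Summary, Section 8). A patient who dies without transfer has no ICU admission and so meets the definition as written. Nothing in either statement removes that patient.

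**Step 2: weight of one death.** With 20 patients randomised 1:1 there are 10 per arm, so one patient is 1/10 = 10 percentage points.

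**Step 3: illustration with assumed counts.** Control: 3 ICU admissions, no ward deaths. Active: 2 ICU admissions and w ward deaths. Literal success is (10 − ICU admissions)/10. Success as alive without ICU is (10 − ICU admissions − ward deaths)/10. Intervals are 95% Clopper-Pearson, the method named in Section 7.1. Control is 7/10 (34.8 to 93.3%) under both definitions.

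| w | Active, as worded | Active, alive without ICU |
|---|---|---|
| 0 | 8/10 (44.4 to 97.5%) | 8/10 (44.4 to 97.5%) |
| 1 | 8/10 | 7/10 (34.8 to 93.3%) |
| 2 | 8/10 | 6/10 (26.2 to 87.8%) |
| 3 | 8/10 | 5/10 (18.7 to 81.3%) |

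As worded, the active arm leads by 10 points whatever w is. With death as failure, the arms tie at w = 1 and the direction reverses from w = 2. The intervals are wide and overlap throughout, so what changes is the direction of the estimate, not a significance decision.

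**Step 4: how likely is any such death?** The documents give no risk of death without ICU transfer. For an assumed risk q, the chance of at least one among 20 patients is 1 − (1 − q)^20:

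- q = 2%: 1 − 0.98^20 = 33%
- q = 5%: 1 − 0.95^20 = 64%
- q = 10%: 1 − 0.90^20 = 88%

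This is the chance that the problem arises at all, in either arm. It is not the chance that the comparison between arms is distorted; equal risk in both arms favours neither on average.

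**Step 5: mortality horizon, side by side.**

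| Place | Horizon |
|---|---|
| Summary, outcome measures | 28 days |
| Summary, secondary endpoint 7 | 28 days |
| Section 10, item 7 | 28 days |
| Section 8, secondary endpoint 7 | 60 days |

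The item keeps the same number and place in the three numbered lists, so this is one endpoint with two horizons.

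**The case against.** Four objections deserve an answer.

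**Death is not scored as success anywhere.** That is correct. A reader might infer that the plan deliberately rewards death, and the documents do not support this. The definition is silent, and Section 10 puts death at the head of its efficacy list. But that list does not redefine the primary endpoint, so the gap remains.

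**Harm would be seen elsewhere.** A reader might infer that plasma causing rapid ward deaths could pass as beneficial. The safety design argues against that. Rapid deterioration on transfusion, TRALI and TACO are primary safety endpoints (Section 8). Death is a serious adverse event (Section 12), and the proportions with such events are compared by Fisher's exact test (Section 7.1.1). The halting criteria in Section 13 require review after a death in the hour following infusion or after one serious event associated with the product. Hospital mortality also captures ward deaths. All of this stands, and it limits the harm. It does not make the primary proportion mean what its name suggests.

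**The other secondary endpoints.** It is tempting to extend the criticism to length of stay, which an early death shortens, and to measures taken in the ICU, such as "Type and duration of respiratory support (and other ICU support) in ICU" and "4. ICU mortality and LOS". The documents do not carry that far. How deaths enter length of stay is a rule that a statistical analysis plan may supply, and the item is listed beside mortality. Section 7.1 makes 10 per arm the default denominator for percentages, so ICU mortality need not be confined to those admitted. Ventilator-free days is already listed. Replacing these measures would be a preference, not a correction.

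**A statistical analysis plan could settle the rest.** For the primary endpoint this is weak: what counts as success, and over what period, is stated in the protocol itself. Nor would an analysis plan alone remove a contradiction between two protocol sections.

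**Conclusion.** The point holds in two parts.

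First, the primary endpoint lacks a survival condition and an end day in both places where it is stated, and its literal reading counts a ward death without ICU transfer as success. Each such death is worth 10 percentage points in its arm. This rests on the wording and on 10 patients per arm, not on any assumed rate. The counts in the illustration and the 2%, 5% and 10% risks are assumptions; the documents contain no estimate of either.

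Second, the 28-day and 60-day horizons contradict each other exactly. A reader might infer that 28 days is right because it appears three times. The text does not settle it: Section 8 is the endpoint section, and Section 4.2 ties study completion to day 60.

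The first part is the more important, because it changes what the trial's main efficacy result can be taken to show.

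**What to change.** 1. State one primary endpoint in the Summary and Section 8: alive and not admitted to ICU from randomisation through a stated day, with death from any cause by that day counted as failure. Day 28 is one workable choice, since the day-28 contact in Section 9 already asks about survival and whether the patient is in the ICU.
2. Report ICU admission and death separately as components, by arm.
3. Reconcile the mortality endpoint across the Summary (both places), Section 8 and Section 10. One way is to list day-28 and day-60 mortality on separate lines and name one of them as the endpoint.

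**Cost.** The change is almost entirely one of wording. Transfer to ICU is already a secondary endpoint, and the day-28 assessments are repeated at days 60 and 90 (Schedule of Events footnote). The day-28 contact records status on that day, so it should also establish whether there was any ICU stay since discharge. The downside is small: the primary endpoint becomes a composite, which is why its components must be shown.
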